6.4.3 Laboratory Tests

Laboratory testing will be conducted at Screening, Baseline, and Weeks 2, 4, 8, 12, 24, 36, and 48, Baseline-Extension, Week 4-Extension, Week 8-Extension, Week 12-Extension, Week 24-Extension, Week 36-Extension, Week 48-Extension and/or early discontinuation. Clinical laboratory evaluations include:

Hematology: hemoglobin, hematocrit, platelets, CBC with differential and absolute neutrophil count, RBC count and indices. At Screening and prior to lumbar puncture: INR, PT and partial PT

Serum Chemistry: sodium, potassium, chloride, calcium, magnesium, ALT, AST, LDH, ALP, GGT, phosphorus, bicarbonate, CPK, total protein, albumin, total bilirubin (if greater than 2 mg/dl bilirubin will be fractionated), glucose, creatinine, BUN, uric acid. TSH, free T3 and free T4. Also, anti-TPO antibodies at Baseline, Week 2, Week 4, Week 8, Week 12, Week 24, Week 36, Week 48, Baseline-Extension, Week 4-Extension, Week 8-Extension, Week 12-Extension, Week 24-Extension, Week 36-Extension, Week 48-Extension and whenever TSH is outside of normal range. Additionally, at Screening: total cholesterol, LDL, HDL, triglycerides, folate, HbA1c, P-Amylase or Lipase; Estimated glomerular filtration rate (eGFR).

Urinalysis (collect urine specimen just prior to obtaining weight): macroscopic examination, pH, specific gravity, ketones, nitrites, urobilinogen, leukocyte esterase, protein, creatinine, glucose, and occult blood. If blood, protein, or leukocytes are positive, microscopic examination will be performed on abnormal findings.

Serum pregnancy test will be conducted at Screening, Baseline, and Weeks 4, 12, 24, 36 and 48, Baseline-Extension, Week 4-Extension, Week 12-Extension, Week 24-Extension, Week 36-Extension, Week 48-Extension and early discontinuation. Urine pregnancy tests will be performed (as well as serum) at Baseline and Baseline-Extension (prior to dosing) and at the discretion of the Investigator. FSH is to be conducted on postmenopausal women at Screening to confirm post-menopausal status.

At Screening Only: HBsAg, HCV (reflex HCV-RNA after a positive HCV Ab), HIV antibody detection, and rapid plasma reagin (RPR). Reflex testing will be done for any positive RPR.

At Screening, Baseline and Baseline-Extension Only: Urine Drug Screen for cannabis (medical and recreational), amphetamines (including MDMA/ecstasy), cocaine, barbiturate, PCP, benzodiazepines, tricyclic antidepressants, and/or opiates. Reflex confirmatory testing will be conducted on all positive urine drug screen samples.

At Screening Only: Urine alcohol level.

For those participating in the optional CSF sub-study, analysis conducted by local lab of cell counts (white blood cells and red blood cells [with reflexed differential if either of the counts is abnormal], CSF protein and CSF glucose.

Clinical laboratory values will be expressed using conventional and standard international (SI) units with normal ranges provided. In the event of repeat values within the same analysis visit, if any measurement has an abnormal result, that measurement will be used for the presentation in by-visit tables. If none of the measurements are abnormal, or all of them are abnormal, the measurement closest to the target day for the analysis visit interval will be used for presentation in by-visit tables. All measurements will be presented in listings and considered for evaluation of potential drug induced liver injury (DILI) or abnormalities.

On-treatment laboratory abnormalities are those with an assessment date after the date/time of first dose of study drug and within 30 days after the last dose of study drug. For the treatment phase, treatment-emergent laboratory abnormalities will be assessed from the date of first dose of study drug until 30 days after the last dose of study drug.

Clinically significant laboratory abnormalities will be identified as Grade 3 to 4 laboratory test results according to CTCAE version 5.0 if available; otherwise according to DAIDS version 2.1 criteria.

Laboratory Test Change from Baseline

The observed value and change from baseline will be summarized for each continuous laboratory parameter in both conventional and SI units.

Laboratory Test Abnormalities

The number and percentage of treated subjects with at least one on-treatment laboratory assessment will be summarized by treatment group (regardless of baseline) for Grade 0, Grade 1 to 2, Grade 3 to 4, Grade 3, and Grade 4. Note that Grade 3 to 4 abnormalities are considered clinically significant.

In addition, the shift from baseline for laboratory abnormalities (based on either normal limits or grading where available) will be tabulated by grade (if applicable), visit, and the overall minimum and maximum observed for treated subjects in the DB and OLE phases. The shift tables will only include subjects with a baseline assessment and at least one on-treatment assessment. For laboratory tests that are not graded, abnormality criteria are specified below (same as used for the listings):

- Low (<lower limit of normal; LLN)
- Normal
- High (>upper limit of normal; ULN)

Liver Function Test Elevations

For the liver function tests, the shift from baseline will be presented by visit and to the maximum observed abnormality for treated subjects in the Randomization and Extension phases. Shift tables will only include treated subjects with an assessment for the specific test of interest at baseline and on treatment.

The following categories will be used to summarize the shift from baseline based on the upper limit of normal (ULN) range for ALT and AST:

- ≤ULN
- >ULN to $\leq 3x$ ULN
- >3x ULN to $\leq 5x$ ULN
- >5x ULN to $\le 10x$ ULN
- 10x ULN to ≤20x ULN
- >20x ULN

The following categories will be used to summarize the shift from baseline based on the ULN range for ALP:

- ≤ULN
- >ULN to ≤ 1.5 x ULN
- >1.5x ULN to $\leq 2.5x$ ULN
- >2.5x ULN

The following categories will be used to summarize the shift from baseline based on the ULN range for BILI:

- ≤ULN
- >ULN to \le 1.5x ULN
- >1.5x ULN to $\leq 2.0x$ ULN
- >2x ULN

The following categories will be used to summarize the shift from baseline based on the ULN range for GGT:

- <ULN
- >ULN to ≤ 2.5 x ULN
- >2.5x ULN

For T3 and T4, the following categories will be used to summarize the shift from baseline:

- <LLN
- >LLN

For TSH, the following categories will be used to summarize the shift from baseline:

- <4 mU/L
- 4-10 mU/L
- >10 mU/L

An evaluation of drug-induced serious hepatotoxicity (eDISH) scatter plot will display the maximum total bilirubin ratio of value to ULN on the y-axis versus the maximum ALT ratio of value to ULN on the x-axis, where the maxima is not necessarily concurrent. Both axes will be on the log10 scale. Ratios < 0.1 x ULN will be set to 0.1. Sample sizes in the legend will represent subjects with paired ratios. A horizontal reference line will be placed at 2 x ULN, and a vertical reference line will be placed at 3 x ULN. The lower left quadrant will be labeled "Normal Range", the upper left quadrant will be labeled "Hyperbilirubinemia", the lower right quadrant will be labeled "Temple's Corollary", and the upper right quadrant will be labeled "Possible Hy's Law Range." The eDISH plot will be produced for treated subjects in the DB Phase and DB and OLE Verdiperstat treated subjects.

Additional listings will be presented for the following:

- All abnormal laboratory values considered potentially clinically significant (Grade 3 or 4) for the DB and OLE phases combined
- Subjects with a maximum value of ALT or AST >3x ULN or a maximum total bilirubin value >2x ULN observed at any point during the entire study, but not necessarily on concurrent visits

6.4.4 Vital Signs and Physical Measurements

Vital signs include systolic blood pressure, diastolic blood pressure, heart rate and temperature.

Physical measurements include height, weight, and BMI.

The observed value and change from baseline in vital signs and physical measurements will be summarized at each visit for the double-blind and OLE phases, separately.

A subject listing of vital signs and physical measurements will be provided for enrolled subjects.

6.4.5 Electrocardiogram

Descriptive statistics for ECG interval data (e.g., RR, QRS, PR, QT, QTcF, QTcB), and ventricular heart rate will be reported by treatment group and visit for the double-blind and OLE phases, separately.

The shift from baseline for ECG interpretation will be tabulated by visit for the double-blind and OLE phases, separately and combined. The shift table will include only subjects with a baseline assessment and at least one on-treatment assessment.

In addition, the number and percentage of subjects with at least one post-treatment QTcF > 450 ms, >480 ms, and >500 ms will be summarized by treatment group and visit for the double-blind and OLE phases, separately and combined. Similar number and percentages will be presented for subjects with at least one post-baseline QTcF change from baseline \geq 30 ms to < 60 ms and those with at least one change from baseline \geq 60 ms.

A by-subject listing of ECG results will be provided for enrolled subjects.

6.4.6 Sheehan-Suicidality Tracking Scale

The S-STS is a prospective, clinician-administered rating scale that contains 16 questions to track both treatment-emergent suicidal ideation and behaviors. The S-STS will be completed on a paper form at the site at Screening, Baseline and each study visit, including Week 48, Baseline-Extension, Week 2-Extension, Week 12-Extension, Week 24-Extension, Week 36-Extension, Week 48-Extension, or early withdrawal. At Screening, the recall period for completing the S-STS is 6 months prior; at all other visits, the recall period for completing the S-STS is since the last visit (two separate versions will be provided). Subjects who have an S-STS score > 0 should be evaluated by the Investigator. If the Investigator determines that a subject is at risk of suicide or self-harm, appropriate measures to ensure the subject's safety and obtain mental health evaluation must be implemented and the Investigator should evaluate if the subject should be discontinued from the study. In the event the subject is unavailable, the S-STS clinician-administered rating scale will be completed that contains 6 yes/no questions.

Self-reported S-STS scores are calculated as follows:

- Ideation subscale score: Sum of scores (0-4) for Questions 2-11
- Behavior subscale score: Sum of scores (0 4) for Questions 1a, (highest of 12 or any row of 16), (highest of 14 or any row of 15), 17, and 20 based on the scoring used for the 2017 version of scale used in this study. In addition, a Behavior subscale score based on the 2019 version of the scoring will also be calculated where the score for a 'Yes' item 20 is 56 and the scores for 18, 19, 21 and 22 are used from the prior visit if applicable.

• Total score: Sum of the ideation and behavior subscale scores. A Total score will be calculated based on both 2017 version and 2019 version.

The self-reported S-STS ideation subscale, behavior subscale, and total score will be summarized as the change from baseline (i.e., <-1, -1, no change, 1, >1) at each visit and the maximum score observed for the double-blind and OLE phases, separately.

All S-STS data will be listed.

6.4.7 Subjects Identified for Narratives

A safety narrative will be prepared for each subject who received at least one dose of Verdiperstat and experienced the following events (regardless of relationship to study drug):

- All deaths on-treatment and post-treatment through the end of the study
- SAEs on-treatment, which includes up to 30 days after the last dose of study drug; SAEs that occur > 30 days (i.e., during the follow-up period) will be included per the clinical judgment of the Biohaven medical monitor
- All premature discontinuations of study drug due to AEs (either identified through "action taken" or "end of treatment status") in subjects who have received at least one dose of Verdiperstat.

These select events are described in the current version (v1.0) of the Biohaven Safety Narrative Scope for BHV-3241 (Verdiperstat). Because select events may be subject to change, updates to the list of events or selection algorithms after database lock may be described in a Note to File (NTF) rather than amending the SAP.

A by-subject listing of safety narrative subject identifiers will be presented for all screened subjects with the select events as described above.

6.4.8 COVID-19 Related Summaries

Analyses are based on the COVID-19 Visit Impact eCRF. At each visit (scheduled or unscheduled) that occur after 01MAR2020, sites complete the COVID-19 Visit Impact eCRF.

COVID-19 visit impact status is based on the response to the lead question "Was this visit impacted by COVID-19 related issues? (yes or no)". If the response to the lead question is "yes", then responses to the following questions are provided:

COVID-19 visit impact type: What was the impact? (check all that apply)

- (1) Missed visit no assessments done
- (2) In-person visit at site (check all that apply)
 - Not all assessments completed *
 - Scheduled visit occurring earlier or delayed relative to protocol specified schedule *
- (3) Remote visit (indicate one)
 - Virtual visit (video/telemedicine) *
 - Telephone contact *

Subcategories marked with "*" are visit impact characteristics.

COVID-19 visit impact relationship: How was the impact related to COVID-19?

- Subject diagnosed with COVID-19 or quarantined due to COVID-19
- Site closed or access restricted due to COVID-19
- Site open but subject unwilling or unable to come to the site due to COVID-19
- Other

COVID-19 visit impact will be tabulated by as-treated treatment group and overall for the safety analysis set for the double-blind and OLE phases, separately. The number and percentage of subjects in the categories defined by COVID-19 visit impact type, visit impact characteristics, and visit impact relationship will be tabulated. Percentages are based on subjects with ≥ 1 visit with non-missing COVID-19 visit impact.

A by-subject listing of COVID-19 visit impact is provided for the enrolled analysis set. The listing displays COVID-19 visit date, study day derived from the COVID-19 visit date, treatment day derived from the COVID-19 visit date, visit impact status, visit type (scheduled or unscheduled), visit impact type, visit impact characteristics, visit impact relationship, and premature study termination (yes; no; not applicable, subject continuing).

7 CONVENTIONS

7.1 Analysis Periods

Analysis periods are defined as follows:

- Screening phase: to include all assessments on or before the first day of study drug.
- Pre-treatment: measurement date/time on or before the study drug first dose date/time. This period is used to derive baseline values.
- On-treatment in the double-blind phase: to include all assessments after the study drug first dose date/time in the double-blind phase and up to the first day of OLE phase study drug or (last day of DB phase study drug + 7 days for efficacy or 30 days for safety), whichever is earliest, for subjects entering OLE or through the double-blind phase study drug last dose date/time + 7 days to assess efficacy endpoints and + 30 days to assess safety endpoints on treatment.
- On-treatment in the OLE phase: to include all assessments after the open label study drug first dose date/time through the study drug last dose date/time + 7 days to assess efficacy endpoints and + 30 days to assess safety endpoints on treatment
- On-treatment in the study: to include any Verdiperstat treatment (double-blind or OLE phase), and all assessments after the first dose date/time up to the last dose date/time + 7 days to assess efficacy endpoints and + 30 days to assess safety endpoints on treatment, excluding the number of days with a dosing break between the double-blind and OLE phases (applicable if dosing break >30 days).

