The number and percentage of subjects who had dose titrations during the OLE phase will also be summarized by time point and dose.

Double-Blind and Open-Label Extension Phases Combined

For the combined phase data, the extent of subject exposure (i.e., treatment duration) to Verdiperstat during the entire study will be quantified as the number of days on study medication (Verdiperstat) and measured from the time the subject received the first dose of Verdiperstat until the time the subject received the last dose of Verdiperstat, either at the end of the study or withdrawal from the double-blind or OLE phases. Treatment Duration includes missed dose days within a study phase and excludes the dosing break between study phases (i.e., (last dose day of Verdiperstat study medication – first dose date of Verdiperstat study medication + 1) – (number of days with a dosing break between the double-blind and OLE phases)).

The extent of subject exposure (i.e., total days on Verdiperstat) during the entire study will also be calculated to exclude days when subjects missed a dose (i.e., Treatment Duration – number of days a subject missed all doses of study medication).

Additionally, percent (%) compliance will be calculated as (total days on Verdiperstat study medication) / (Treatment Duration of Verdiperstat study medication) × 100.

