6.4.1 Adverse Events

AEs will be coded using MedDRA and displayed in tables and listings by system organ class (SOC) and preferred term (PT), unless specified otherwise.

Analyses of AEs will be performed for those events that are considered treatment-emergent AEs (TEAEs), where treatment-emergent is defined as any AE that developed, worsened, or became serious on or after first dose of study drug and prior to 30 days after the last dose of study drug.

A TEAE overview without SOC and PT will be presented as the number and percentage of subjects with any of the following TEAEs: TEAE leading to death; serious TEAE; serious TEAE related to study drug; TEAE leading to study drug discontinuation; any TEAE; TEAE related to study drug; and severe AE.

In addition, TEAEs will be tabulated by SOC and PT for all treated subjects for the following endpoints for the DB and OLE phases, separately and combined:

- TEAEs
- TEAEs related to treatment (includes, possibly related and related)
- TEAEs by highest severity (mild, moderate, severe)

- TEAEs related to treatment by highest severity
- Treatment-emergent SAEs
- TEAEs leading to discontinuation of study treatment

In the above tabulations, each subject will contribute only once (i.e., the most related occurrence or the most severe occurrence) to each of the incidence rates in the descriptive analysis, regardless of the number of episodes.

The TEAEs summary by SOC and PT will also include the number of unique AE occurrences; unique occurrences mean that if a subject had an AE twice, both will be reported (i.e., the subject will contribute twice to the count of events).

All AEs occurring pre-treatment and during the entire study will be listed. Additional listings will be provided including deaths, SAEs, AEs leading to discontinuation of study drug, and events of special interest (see Section 6.4.2).

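### For breaks over 30 days, SAP 7.1 removes from the combined on-treatment period days that its double-blind definition counts, and the SAP does not say whether 7.1 or the windows in 6.4.1 and 6.4.3 govern the combined tables

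*SAP*

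**What the plan says.** SAP 7.1 gives three on-treatment definitions. Two matter here.

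- **Double-blind phase.** For subjects who go on to the extension, the window closes at the first OLE dose or at "last day of DB phase study drug + 7 days for efficacy or 30 days for safety), whichever is earliest, for subjects entering OLE". Safety data in the first 30 days off drug are therefore on-treatment unless the OLE starts sooner.
- **Whole study (combined).** The entry opens "On-treatment in the study: to include any Verdiperstat treatment (double-blind or OLE phase), and all assessments after the first dose date/time up to the last" (the sentence runs on to the final dose, with 7 days added for efficacy and 30 for safety). It then qualifies the period: "excluding the number of days with a dosing break between the double-blind and OLE phases (applicable if dosing break >30 days").

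Three other places bear on the same days.

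- SAP 6.2.6.1, on combined exposure, subtracts the "number of days with a dosing break between the double-blind and OLE phases" and states the rule in words: "Treatment Duration includes missed dose days within a study phase and excludes the dosing break between study phases". There is no 30-day threshold.
- SAP 6.4.1 defines a treatment-emergent event as one arising "on or after first dose of study drug and prior to 30 days after the last dose of study drug". It asks for tables by phase and combined, and does not mention the break. The on-treatment laboratory window in SAP 6.4.3 does not mention it either.
- SAP 6.1.1.1 draws the combined tables from both phases for subjects randomized to verdiperstat, and from the OLE alone for subjects randomized to placebo.

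**The concern.** A combined period should contain every day that its component periods contain. As worded, the combined period in 7.1 does not: once the break passes 30 days, the post-dose follow-up of the double-blind phase drops out. The combined verdiperstat table is the all-exposure safety summary, so it could omit a serious event that the double-blind table reports. The days removed are those just after stopping drug.

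Long breaks are foreseeable. Protocol 4.5.2 lets subjects who finished before their site opened the OLE enter up to about 12 weeks after it opens, whenever they completed. Protocol 8.1.4 requires serious events to be collected for 30 days after dosing stops, and SAP 6.4.7 treats serious events in those 30 days as on-treatment for narratives. The plan thus regards these days as relevant elsewhere.

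**Working it through.** The plan states no figure on this point, so there is none to reproduce. The check counts days under each definition.

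**Inputs.** Let B be the number of drug-free days between the last double-blind dose and the first OLE dose, for a subject randomized to verdiperstat. Let w be the post-dose window in SAP 7.1: 30 days for safety, 7 for efficacy.

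**Break days counted**

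- Double-blind definition: min(w, B).
- Combined definition, literal: B if B ≤ 30; 0 if B > 30.
- Union of the double-blind and OLE windows: min(w, B).

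The literal reading takes the break to mean the whole break. SAP 6.2.6.1 uses the same phrase that way, and nothing in 7.1 keeps the first 30 days.

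| Break B (days) | Safety: double-blind | Safety: combined | Efficacy: double-blind | Efficacy: combined |
|---|---|---|---|---|
| 7 | 7 | 7 | 7 | 7 |
| 10 | 10 | 10 | 7 | 10 |
| 28 | 28 | 28 | 7 | 28 |
| 30 | 30 | 30 | 7 | 30 |
| 31 | 30 | 0 | 7 | 0 |
| 60 | 30 | 0 | 7 | 0 |
| 120 | 30 | 0 | 7 | 0 |

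**Safety.** The two definitions agree up to B = 30. From B = 31 the combined period loses 30 − 0 = 30 days that the double-blind period counts. For a subject completing both 48-week phases, the union has 336 + 30 + 336 + 30 = 732 safety days, so the loss is 30/732 = 4.1%.

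**Efficacy.** Above 30 days, 7 days are lost. Between 8 and 30 days the error runs the other way: at B = 30 the combined period counts 30 − 7 = 23 days too many. This is a minor consequence of pairing a 30-day trigger with a 7-day window.

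**Which section governs.** Take a 90-day break and two adverse events, 10 and 60 days after the last double-blind dose.

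| Rule | Day 10 | Day 60 |
|---|---|---|
| Double-blind period, 7.1 | counted | not counted |
| Combined period, 7.1 literal | not counted | not counted |
| 6.4.1, last dose = final OLE dose | counted | counted |
| Union of phase windows | counted | not counted |

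The 7.1 rule under-counts and this reading of 6.4.1 over-counts. Neither matches the union, which leaves no mismatch with the double-blind definition at any break length in the first table.

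**The case against.** The strongest reply is that 7.1 may not drive the combined tables at all. Sections 6.4.1 and 6.4.3 carry their own windows, without a break exclusion, and 6.1.1.1 says combined statistics use both phases. On that view the day-10 event stays in. This stands as far as it goes: a reader might infer from 7.1 that such events are certain to disappear, and the documents do not establish that. It does not settle the matter, because with last dose read as the final OLE dose it admits events long after drug was stopped. Reading last dose separately for each phase would give the union, but 6.4.1 does not say so.

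A second reply is that the 30-day trigger matches the 30-day safety window, so the intent was probably to exclude only days beyond it. That is plausible, and for safety keeping breaks of 30 days or less is correct. The text does not express that intent.

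A third is that the reach is small. This is largely right. Once a site is open, completers who choose the OLE must enter directly at Week 48, so long breaks arise only for those who finished earlier. For efficacy, the only scheduled assessment likely to be misplaced is a Baseline-Extension visit after a break of about 28 to 30 days. SAP 6.3 already treats that visit as an OLE baseline and plans no inference for the OLE.

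**Conclusion.** The point holds as an internal inconsistency in the combined on-treatment definition. For subjects randomized to verdiperstat who enter the OLE after more than 30 days off drug, the literal 7.1 rule removes 30 safety days and 7 efficacy days that the double-blind rule counts. The SAP also leaves open whether that rule or the windows in 6.4.1 and 6.4.3 apply to the combined tables. The conclusion assumes the whole-break reading, which 6.2.6.1 supports.

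Three stronger inferences are tempting but not supported.

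- **A number of lost events.** The documents give neither the number of late entrants nor event rates, so none can be computed. Most of these tables also count each subject once.
- **Missing QTcF outliers.** The Week 48 dose is given in clinic (Protocol 4.3.3), and the next scheduled ECG is at Baseline-Extension. After a break over 30 days, that ECG is already outside the double-blind window. Only unscheduled ECGs could be lost.
- **A fault in the exposure definition.** Events counted after the last dose but outside treatment duration are normal in every phase of this plan. The union would keep such a tail too.

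The double-blind tables and the by-subject listings retain every event, and no primary or key secondary result changes.

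**What to change.** In SAP 7.1, define the combined period as the union of the double-blind verdiperstat on-treatment period and the OLE on-treatment period. For any break length, this excludes only days that fall after the last double-blind dose + 30 days (safety) or + 7 days (efficacy) and before the first OLE dose. Delete the parenthetical with the 30-day trigger. In 6.4.1 and 6.4.3, refer the combined-phase adverse event and laboratory windows to this definition, so that one rule governs.

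The cost is one rewritten sentence, two cross-references and a date condition in the combined-phase programs. No new data are needed, and the double-blind efficacy analysis is untouched.
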